5.5.2. Estimands

Unless otherwise specified, the attributes and strategies for the ICEs that were used for the primary estimand of the primary endpoint (Estimand 1, Section 5.3.2) will also be used for the estimand for each of the other endpoints (Section 5.5).

ICE categories 1-3 will be handled by the **composite strategy**. ICE category 4 will be handled by the **hypothetical strategy** (as if participants would have not experienced this intercurrent event), and ICE category 5 will be handled by the **treatment policy strategy**. To be more specific,

- Participants with an ICE in category 1-3 prior to a visit will be considered, at that visit and all subsequent visits, as **not having achieved the binary endpoints for binary endpoints** and as **having no change from baseline (i.e., the baseline value will be assigned) for continuous endpoints**.
- Participants with an ICE 4 will have their observed data set to missing at all visits after the ICE 4.
- Participants with an ICE 5 will have their observed data used after the ICE 4 used, if available.
- For participants experiencing multiple ICEs, ICEs in categories 1-3 will override ICEs 4 and 5.

5.5.3. Estimators (Analyses) for Estimands

Unless otherwise specified, the other endpoints presented in Section 5.5 will be analyzed based on the FAS (Section 2.2.2) according to randomized study intervention regardless of the study intervention actually received.

Descriptive statistics (i.e., mean, median, SD, IQ range, minimum, and maximum) will be used to summarize continuous endpoints and counts and percentages will be used to summarize binary endpoints by visit.

Treatment comparisons between combination therapy versus each monotherapy will be performed by visit through Week 38. All statistical testing will be performed at the 2-sided significance level of 0.2. No adjustment for multiple comparisons will be made for these other endpoints. Nominal p-values will be presented.

Binary Endpoints

After accounting for the ICEs, participants with missing status for a binary endpoint will be considered not to have achieved the associated binary endpoint (i.e. nonresponder imputation).

Binary endpoints will be summarized with the number and frequency of participants who achieve the endpoint by treatment group. Treatment comparisons (combination therapy versus each monotherapy) will be performed using analyses suitable for categorical data (e.g., a CMH chi-square test stratified by corticosteroid use at baseline, as appropriate) to compare the proportion of participants achieving the endpoints. In case of rare events, the Fisher's exact test will be used for treatment comparisons.

Continuous Endpoints

For continuous endpoints that are assessed only at one post-baseline visit (e.g., change from baseline in Mayo score and change from baseline in modified Mayo score at the Week 12 DBL), the missing data after accounting for ICEs will be imputed by the MI methods as described in [Table 3](#). The MI will be performed on each Mayo subscore with missing data and then the Mayo scores will be derived from such imputed subscores. These endpoints will be compared between combination therapy versus each monotherapy using an analysis of covariance (ANCOVA) with treatment group, corticosteroid use at baseline (yes, no), and baseline score as the explanatory factors.

For continuous endpoints that are assessed at more than one post-baseline visit, to account for the missing data after the ICEs have been accounted for, a MMRM will be used, under the assumption of MAR, to test the treatment difference between combination therapy versus each monotherapy. In MMRM, missing data will not be imputed, but rather missing data will be accounted for through correlation of repeated measures in the MMRM model. If the MMRM normality assumption is in question, an appropriate transformation may be implemented before fitting the MMRM model.

The explanatory variables of the MMRM model will include treatment group, corticosteroid use at baseline (yes, no), visit, respective baseline score, and an interaction term of visit with treatment group. An unstructured covariance matrix for repeated measures within a subject will be used. The F-test will use Kenward-Roger's approximation for degree of freedom. In case of lack of convergence, empirical structured covariances will be used in the following order until convergence is reached: 1) Toeplitz; 2) first order Autoregressive Moving Average. The treatment difference between combination therapy and each monotherapy will be estimated by the difference in the least squares means (LSmeans). The 80% CI for the difference in LSmeans and p-values will be calculated based on the MMRM.

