5.3.1.1. Mayo Score, Partial Mayo Score, and Modified Mayo Score

The **Mayo score** was developed from the criteria of Truelove and Witts¹⁴ for mild, moderate, and severe UC and from the criteria of Baron et al² for grading endoscopic appearance. The Mayo score consists of the following 4 subscores:

- Stool frequency
- Rectal bleeding
- Findings of endoscopy
- Physician's global assessment (PGA)

Each subscore is rated on a scale from 0 to 3, indicating normal to severe activity, as defined in Attachment 1.

The **Mayo score** is calculated as the sum of the 4 subscores (stool frequency, rectal bleeding, PGA, and endoscopy findings) and ranges from 0 to 12 points. A score of 3 to 5 points indicates mildly active disease, a score of 6 to 10 points indicates moderately active disease, and a score of 11 to 12 points indicates severely active disease.

The **partial Mayo score**, which is the Mayo score without taking into account the findings of endoscopy, is calculated as the sum of stool frequency, rectal bleeding, and PGA subscores, and may take on values from 0 to 9.

The **modified Mayo score**, which is the Mayo score without the PGA subscore, is calculated as the sum of the stool frequency, rectal bleeding, and endoscopy subscores, and may take on values from 0 to 9.

Due to the requirement for endoscopy findings for the evaluation of the Mayo score, it is not feasible to evaluate the Mayo score at each scheduled visit in the study. Therefore, the Mayo score will be evaluated at Weeks 0, 12 and 38, and the partial Mayo score will be evaluated at the other

study visits. The modified Mayo score can be derived from the Mayo score and is not a separate evaluation.

Mayo Rectal Bleeding and Stool Frequency Subscores

The eCRFs capture seven days of rectal bleeding data and the number of stools per day prior to each visit at which the Mayo score or partial Mayo score is collected. Data from 3 of these 7 days are used to calculate the Mayo rectal bleeding and stool frequency subscores; sites are instructed to check the boxes next to the 3 days which are used (see [below](#) for information on what days the sites are instructed to use).

The Mayo rectal bleeding subscore is calculated as the average rectal bleeding number for the three days based on the criteria in Attachment 1.

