5.5. Other Efficacy Endpoints

In addition to the primary and major secondary endpoints, other efficacy endpoints related to disease status, HRQoL outcomes (including fatigue), and inflammatory biomarkers will also be analyzed. This section outlines the definitions (Section 5.5.1) and analyses (Section 5.5.2) of the other efficacy endpoints.

Clinical Endpoints

- Clinical response at Week 38

-
- Clinical response at Week 38 by clinical response status at Week 12
 - Clinical remission at Week 38
 - Clinical remission at Week 38 by clinical remission status at Week 12
 - Clinical remission at Week 38 by clinical response status at Week 12
 - Change from baseline in Mayo score at Weeks 12 and 38.
 - Change from baseline in partial Mayo score by visit through Week 38.
 - Change from baseline in modified Mayo score at Weeks 12 and 38.
 - Change from baseline in Mayo subscores by visit through Week 38.
 - Modified Mayo response at Weeks 12 and 38
 - Modified Mayo response at Week 38 by modified Mayo response status at Week 12
 - Symptomatic remission by visit through Week 38
 - Endoscopic healing at Weeks 12 and 38
 - Endoscopic healing at Week 38 by endoscopic healing status at Week 12
 - Endoscopic normalization at Weeks 12 and 38.
 - Endoscopic normalization at Weeks 38 by endoscopic normalization status at Week 12
 - Clinical response, clinical remission, and endoscopic healing at Weeks 12 and 38 by negative response signature status at baseline.
 - Clinical remission by alternative definitions:
 - Clinical remission (UNIFI definition) at Weeks 12 and 38
 - Clinical remission (UNIFI definition) at Week 38 by clinical remission (UNIFI definition) status at Week 12
 - Clinical remission (Health Authority definition 1) at Weeks 12 and 38
 - Clinical remission (Health Authority definition 1) at Week 38 by clinical remission (Health Authority definition 1) status at Week 12
 - Clinical remission (Health Authority definition 2) by visit at Weeks 12 and 38
 - Clinical remission (Health Authority definition 2) at Week 38 by clinical remission (Health Authority definition 2) status at Week 12
 - Histologic healing at Weeks 12 and 38
 - Mucosal healing at Weeks 12 and 38
 - Histologic remission at Weeks 12 and 38
 - Histologic-endoscopic mucosal healing at Weeks 12 and 38
 - Deep histologic-endoscopic mucosal healing at Weeks 12 and 38
 - Geboes total score, high activity subscore, and low activity subscore at Weeks 0, 12, and 38

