5.6. Exploratory Endpoints

Exploratory endpoints include:

- Change from baseline in average daily number of BSFS types 6 and 7 stools by visit through Week 12
- Change from baseline in average daily number of BSFS types 5, 6, and 7 stools by visit through Week 12
- A ≥ 2 reduction in average daily number of BSFS types 6 and 7 stools by visit through Week 12

- $A \geq 2$ reduction in average daily number of BSFS types 5, 6, and 7 stools by visit through Week 12
- Proportion of participants in each category of Patient's Global Impression of Change (PGIC) of Severity of UC by visit through Week 38
- $A \geq 1$ -point improvement in PGIC by visit through Week 38
- $A \geq 2$ -point improvement in PGIC by visit through Week 38

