5.6.3. Estimators (Analyses) for Estimands

Unless otherwise specified, exploratory endpoints presented in Section 0 will be analyzed based on the FAS (Section 2.2.2) according to randomized study intervention regardless of the study intervention actually received.

Descriptive statistics (i.e., mean, median, SD, IQ range, minimum, and maximum) will be used to summarize continuous endpoints and counts and percentages will be used to summarize binary endpoints by visit.

Treatment comparisons between combination therapy versus each monotherapy will be performed by visit through Week 38. No adjustment for multiple comparisons will be made for these other endpoints. Nominal p-values will be presented.

Binary Endpoints

After accounting for the ICEs, participants with missing status for a binary endpoint will be considered not to have achieved the associated binary endpoint (i.e. nonresponder imputation). Treatment comparisons (combination therapy versus each monotherapy) will be performed using analyses suitable for categorical data (e.g., a CMH chi-square test stratified by corticosteroid use at baseline, as appropriate) to compare the proportion of participants achieving the endpoints. In case of rare events, the Fisher’s exact test will be used for treatment comparisons.

Continuous Endpoints

After accounting for the ICEs, to account for the missing data for continuous endpoints, a MMRM as described in Section 5.5.3 will be used, under the assumption of MAR, to test the treatment comparison between combination therapy versus each monotherapy. In MMRM, missing data will not be imputed, but rather missing data will be accounted for through correlation of repeated measures in the model. If the normality assumption is in question, an appropriate transformation may be implemented before fitting the MMRM model.

Ordinal Endpoints

After accounting for the ICEs, treatment comparisons (combination therapy versus each monotherapy) will be performed using a CMH chi-square test (Row Mean Scores) stratified by corticosteroid use at baseline (yes, no).

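### The MMRM in SAP 5.5.3 fits one baseline slope across all visits of an endpoint; a baseline-by-visit term would guard against a small, conditional loss of precision at almost no cost.

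*SAP*

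**What the plan says.** SAP 5.5.3 gives the complete list of fixed effects: the model "will include treatment group, corticosteroid use at baseline (yes, no), visit, respective baseline score, and an interaction term of visit with treatment group". On the covariance it says "An unstructured covariance matrix for repeated measures within a subject will be used", with Kenward-Roger degrees of freedom and two fallback structures if the fit does not converge. On use of the model it says "Treatment comparisons between combination therapy versus each monotherapy will be performed by visit through Week 38" and "All statistical testing will be performed at the 2-sided significance level of 0.2", with nominal p-values and no multiplicity adjustment.

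The number of visits sharing a slope differs by endpoint.
- Partial Mayo has the longest series: "Change from baseline in partial Mayo score by visit through Week 38". By the protocol's Schedule of Activities this is 16 post-baseline visits, Weeks 2 to 38.
- IBDQ has Weeks 6, 12, 24 and 38.
- Full Mayo has two post-baseline visits: "the Mayo score will be evaluated at Weeks 0, 12 and 38, and the partial Mayo score will be evaluated at the other" study visits.

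For an endpoint with only one post-baseline visit, SAP 5.5.3 uses an ANCOVA with baseline score as a covariate, and gives change in Mayo at the Week 12 lock as an example. That model has its own Week 12 slope.

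SAP 5.6.3 reuses the model for exploratory endpoints ("a MMRM as described in Section 5.5.3 will be used"), but the only continuous ones are the BSFS averages, such as "Change from baseline in average daily number of BSFS types 6 and 7 stools by visit through Week 12".

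Under SAP 5.5.2, a participant with an ICE in categories 1-3 is assigned the baseline value from then on, so the change from baseline is zero.

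**The concern.** The model lets the treatment effect differ by visit but holds the baseline effect fixed. If early scores follow baseline more closely than late scores do, the slope of change on baseline differs between Week 2 and Week 38. The fitted common slope is then a weighted average that is somewhat wrong at the ends of the series. Where it is wrong, removable variance stays in the treatment comparison.

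The plan also handles one estimate in two ways. Change in Mayo at Week 12 is adjusted with its own slope at the Week 12 lock. Once Week 38 data exist, Mayo has two post-baseline visits and falls under the MMRM, where Weeks 12 and 38 share a slope.

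At stake is the width of confidence intervals for secondary continuous endpoints, including those that describe the monotherapy phase.

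**Working it through.** **Stated figure.** The only power figures in the documents concern clinical response (protocol 9.2, Table 4; SAP 1.4, Table 1). Simulating three binomial arms of 70, with both comparisons required at 1-sided 0.1, gives 81.4% against the stated 81% for 55%/55%/75%. The other five rows agree within 0.3 points. No power or precision figure is given for the MMRM endpoints, so there is none to reproduce.

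**Inputs from the documents.** 70 per arm, 1:1:1; fixed effects and unstructured covariance as listed; 16, 4 or 2 visits; zero change after ICE 1-3.

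**Inputs assumed.** Correlation of score with baseline at each visit, SD by visit, and residual correlation between visits.

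**Formula.** With visit-by-treatment in the model and complete data, the estimated effect at visit t is (difference in mean change) minus slope × (difference in mean baseline). Using a common slope b in place of the true slope β_t multiplies the variance by

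VR_t = 1 + (β_t − b)² × Var(baseline) / σ_t²,

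where σ_t² is the residual variance, b = 1'S⁻¹β / 1'S⁻¹1, and S is the residual covariance. Slopes below are for the score; the slope of change is one less, so differences between slopes are the same.

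**Two visits by hand (full Mayo).** Take all SDs as 1, baseline correlation 0.5 at Week 12 and 0.2 at Week 38, and residual correlation 0.5.
- Residual variances: 1 − 0.25 = 0.75 and 1 − 0.04 = 0.96. Covariance: 0.5 × √(0.75 × 0.96) = 0.424.
- Weights: 0.96 − 0.424 = 0.536 and 0.75 − 0.424 = 0.326.
- b = (0.536 × 0.5 + 0.326 × 0.2) / 0.862 = 0.387.
- Week 12: 1 + 0.113² / 0.75 = 1.017. Week 38: 1 + 0.187² / 0.96 = 1.036.

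Over the patterns tried, Week 38 VR is 1.013-1.046 for two visits and 1.016-1.054 for four visits (IBDQ).

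**Sixteen visits (partial Mayo), by formula at Week 38, no ICEs.** Baseline correlation falls linearly; SD is constant or grows 30%; residual correlation is constant at 0.5, autoregressive, or a mixture.
- 0.5 to 0.3: 1.004-1.022.
- 0.5 to 0.1: 1.040-1.101.
- A constant residual correlation of 0.7 gives more: 1.017-1.034 and 1.168-1.183 for the same two patterns. The extreme of the grid, 0.7 to 0.2 with constant 0.7, gives 1.51.

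**Sixteen visits, simulated** (210 participants, iterated GLS with unstructured covariance, mixture residual correlation, constant SD, 1,500 runs each). Variance under the common slope divided by variance under visit-specific slopes:

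| Baseline correlation | ICE 1-3 by Week 38 | Week 2 | Week 12 | Week 38 |
|---|---|---|---|---|
| 0.5 throughout | 0% | 1.000 | 0.999 | 0.994 |
| 0.5 to 0.3 | 0% | 1.015 | 1.007 | 1.007 |
| 0.6 to 0.3 | 0% | 1.025 | 1.001 | 1.035 |
| 0.6 to 0.2 | 0% | 1.021 | 1.000 | 1.056 |
| 0.6 to 0.3 | 20% | 1.008 | 0.999 | 1.010 |
| 0.6 to 0.2 | 20% | 1.017 | 0.998 | 1.035 |

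Assigning zero change after ICE 1-3 pulls the late slope of change toward zero (from −0.70 to −0.56 in the 0.6 to 0.3 case), which shrinks the loss. Week 2 can lose about as much as Week 38; Week 12 loses almost nothing.

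**What it means for a test.** A comparison with 80% power at 2-sided 0.2 has signal-to-SE 1.282 + 0.842 = 2.123. At VR 1.05, power is Φ(2.123/√1.05 − 1.282) = 78.5%. At 1.03 it is 79.1%, and at 1.10 it is 77.1%. CI width grows by √1.035 − 1 = 1.7% at VR 1.035 and by 4.9% at 1.10.

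**Price of the extra term.** 16 − 1 = 15 more fixed effects for partial Mayo. If the slopes are equal, the cost per visit is about 1/(210 − 5) = 0.5% of variance.

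**The case against.** The model is valid and pre-specified, and nothing in the documents shows that the slope changes. There are no SDs by visit and no baseline-to-visit correlations, so the loss may be zero. The estimand's own rule for ICE 1-3 reduces it in the scenarios where it arises. The endpoints concerned are non-primary and nominal, and many Week 38 endpoints are binary and not analysed by this model. Partial Mayo already needs 16 × 17 / 2 = 136 covariance parameters, and the SAP provides for non-convergence.

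All of this stands, and it sets the size of the point. It does not remove the point: equal slopes over 16 visits is itself an assumption that the plan does not need. The steroid taper from Week 6, the change of regimen in the combination arm after Week 12 and the growing share of zero changes after ICE 1-3 all give reason not to presume it.

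A reader might infer more than this supports:
- **A certain loss, confined to late visits.** It is conditional, and the common slope can be off at Week 2 as well.
- **Bias.** Allocation is randomised, and with complete data the simulations showed none. Residual baseline imbalance is the same quantity as the variance inflation, not an additional harm.
- **Week 38 exploratory endpoints affected through SAP 5.6.3.** Its continuous endpoints stop at Week 12.
- **A need for a corticosteroid-stratum-by-visit term.** The taper makes it plausible, but no calculation here supports it, and it would add another 15 fixed effects for partial Mayo.

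**Conclusion.** The omission is a fact of the text; its cost is conditional and small. With no intercurrent events, the Week 38 variance is about 0-10% too large under mild to moderate assumed decay of the baseline correlation. With 20% ICE 1-3 and the baseline value assigned, it is about 1-3.5% too large in the scenarios simulated. With equal slopes there is no loss. Larger figures need a steep decay, a high constant residual correlation between visits, or both. These ranges rest on assumed correlations and SDs and on data complete apart from ICEs. The primary and major secondary endpoints are untouched and the trial's conclusion does not depend on this. It is worth changing only because the change costs so little.

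**What to change.** In SAP 5.5.3, add the interaction of baseline score with visit to the MMRM's explanatory variables. For full Mayo this also gives Week 12 its own slope, as in the Week 12 lock ANCOVA. The cost is one model term and no new data: 15 extra fixed effects for partial Mayo, 3 for IBDQ and 1 for full Mayo, and at most about 0.5% of variance if the slopes are equal. The existing fallback for non-convergence can stay as it is. SAP 5.6.3 would inherit the term but gain little. A stratum-by-visit term is optional. Make the change before the Week 38 data are unblinded for analysis.

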5.6. Exploratory Endpoints

Exploratory endpoints include:

- Change from baseline in average daily number of BSFS types 6 and 7 stools by visit through Week 12
- Change from baseline in average daily number of BSFS types 5, 6, and 7 stools by visit through Week 12
- A ≥ 2 reduction in average daily number of BSFS types 6 and 7 stools by visit through Week 12

- $A \geq 2$ reduction in average daily number of BSFS types 5, 6, and 7 stools by visit through Week 12
- Proportion of participants in each category of Patient's Global Impression of Change (PGIC) of Severity of UC by visit through Week 38
- $A \geq 1$ -point improvement in PGIC by visit through Week 38
- $A \geq 2$ -point improvement in PGIC by visit through Week 38

5.6.1. Definitions

5.6.1.1. Bristol Stool Form Scale

The **BSFS** is a medical aid to classify the form (or consistency) of human feces into 7 categories⁵. It has been used as a research tool to evaluate the effectiveness of treatments for various diseases of the bowel (e.g., irritable bowel syndrome). Participants will complete the BSFS as a daily diary entry from Week 0 through Week 12.

Average number of BSFS types 6 and 7 stools per day is defined as: the sum of number of BSFS types 6 and 7 stools in previous 7 days in a dairy card \div total days assessment performed. Similarly, average number of BSFS types 5, 6 and 7 stools per day is defined as: the sum of number of BSFS types 5, 6 and 7 stools in previous 7 days in a dairy card \div total days assessment performed. Average number of BSFS stools per day at a scheduled visit will not be calculated if total days of assessment is less than 5 within the previous 7 days prior to a scheduled visit.

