8.1.1. Mayo Score and Partial Mayo Score

The **Mayo score** (see Appendix 8 [Section 10.8]) was developed from the criteria of Truelove and Witts⁶⁴ for mild, moderate, and severe UC and from the criteria of Baron et al³ for grading endoscopic appearance. The Mayo score is calculated as the sum of 4 subscores (stool frequency, rectal bleeding, physician's global assessment, and endoscopy findings) each with a score range of 0 (normal activity) to 3 (severe activity) and a total score range of 0 to 12 points. A score of 3 to 5 points indicates mildly active disease, a score of 6 to 10 points indicates moderately active disease, and a score of 11 to 12 points indicates severely active disease. The endoscopic findings will be assessed by the investigator (ie, local endoscopist) during the endoscopy procedure and by the central reader reviewing a video of the endoscopy. Participant eligibility at baseline will be based on the final reported endoscopic subscore as determined by the following process:

- If the local endoscopist and the central reader agree on the endoscopic subscore, the agreed score will be the final reported endoscopic subscore.
- If there is a discrepancy between the local endoscopist and the central reader subscores, the video endoscopy will be submitted to a second central reader (designated for adjudication). The median score of the 3 completed reads (ie, local read, central read 1, and central read 2 designated for adjudication) will be the final reported endoscopic subscore.

Specific details will be provided in the imaging charter.

Mayo scores are calculated using the following:

1. The stool frequency and rectal bleeding data from the most recent consecutive 3-day period within the 1 week before the visit. The average of the 3-day period will be used to calculate the stool frequency and RBSs for the visit. Days on which the following conditions are met should be excluded from the calculation:
 - a. The day on which medications for constipation, diarrhea, or irregularity were taken. (For participants maintained on a stable dose of bulking or stool-softening agents throughout the study, the days on which these agents are taken should not be excluded from consideration in calculating the Mayo score.)
 - b. The day(s) of a procedure or preparation for a procedure (eg, enemas, other laxatives, a clear liquid diet) that would affect bowel frequency and/or blood content of the stool.

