The Mayo stool frequency subscore is calculated as follows: The absolute stool number is the average of the daily stool number over the three days. At the screening visit, each person indicates the number of stools he/she passed in a 24-hour period when in remission or before his/her UC diagnosis. The stool frequency subscore will be calculated based on the criteria in Attachment 1 by subtracting the number of stools when in remission or prior to UC from the absolute stool number.

Instructions on which 3 days to use in the calculation of the Mayo rectal bleeding and stool frequency subscores: Sites are directed to use the most recent 3 consecutive days within the 7 days prior to the visit and are directed to exclude the following:

- The day medications were taken for constipation, diarrhea or irregularity
- The day of a procedure or preparation for procedure (e.g. enema, other laxatives, or clear liquid diet) that would affect stool frequency and/or blood content of the stool
- The 48 hours after the use of antimotility agents (e.g. diphenoxylate hydrochloride with atropine sulfate or loperamide)
- The 48 hours immediately following a colonoscopy

If 3 consecutive days are not available, the sites are instructed to choose 2 consecutive days and the closest nonconsecutive day. If 2 consecutive days are not available, then 3 nonconsecutive days closest to the visit should be chosen. If 3 days (within the 7 days prior to the indicated visit) that meet the criteria defined above are not available, then the absolute stool number, stool frequency subscore, and rectal bleeding subscore cannot be calculated and will be missing in the eCRF.

Mayo Endoscopy Subscore

The endoscopic findings will be based on the criteria of the Mayo endoscopy subscore described in Attachment 1. The endoscopic findings will be assessed by the investigator (ie, local endoscopist) during the endoscopy procedure and by the central reader reviewing a video of the endoscopy. The endoscopy may be either a colonoscopy or sigmoidoscopy. A full colonoscopy will replace a sigmoidoscopy if screening for polyps or dysplasia is required. The central reader

will also perform a friability assessment (yes, no) for each endoscopy, except for those with an assessed endoscopy subscore of 0, which requires that no friability is present.

Participant eligibility at baseline will be based on the **final reported endoscopic subscore** as determined by the following process:

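### The BSFS loose-stool average keeps bowel-preparation and endoscopy days that the Mayo derivation drops, so Week 12 (and optional Week 4) values can be inflated when those days fall in the diary week

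*SAP*

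**What the plan says.** SAP 5.6.1.1 takes "the sum of number of BSFS types 6 and 7 stools in previous 7 days in a dairy card" and divides by the number of days with an assessment. The same rule serves types 5 to 7. Its only restriction is a minimum: the average "will not be calculated if total days of assessment is less than 5 within the previous 7 days prior to a scheduled visit". Protocol 8.1.8 and the diary text in Protocol Section 8 ask for daily BSFS entries from Week 0 to Week 12 and name no days to leave out.

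The Mayo stool-frequency and rectal-bleeding subscores also come from the 7 days before the visit, with explicit exclusions. SAP 5.3.1.1 removes "The day of a procedure or preparation for procedure (e.g. enema, other laxatives, or clear liquid diet) that would affect stool frequency" and "The 48 hours immediately following a colonoscopy". Protocol 8.1.1, items 1b and 1d, does the same; item 1b covers "The day(s) of a procedure or preparation for a procedure (eg, enemas, other laxatives, a clear liquid diet) that would affect bowel frequency".

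The Schedule of Activities (Protocol Table 1) places an endoscopy and a BSFS reading together at Week 12 for everyone, and at Week 4 for participants in the optional sub-study. Week 10 has a BSFS reading and no endoscopy. SAP 5.6 lists four BSFS endpoints: mean change and a reduction of at least 2 stools/day, each for types 6–7 and types 5–7. SAP 5.6.3 reports nominal p-values without multiplicity adjustment.

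**The concern.** The plan treats the same diary day as unusable for one stool measure and usable for another, and gives no reason. The ground it gives for the Mayo exclusion, that preparation and procedures alter stool frequency, applies at least as strongly to a count of loose and liquid stools.

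If preparation falls in the 7 days before Week 12, its stools enter the average as if they were symptoms. The Week 12 mean can then rise in every arm and look like a worsening since Week 10. Fewer participants reach the 2-stool reduction, and the difference between arms in that rate can narrow.

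**Working it through.** **Plan's own figure.** The documents state no mean, standard deviation, expected effect or power for BSFS, so there is nothing of the plan's to reproduce here. The design power of 81% (Protocol Table 4: 55%/55%/75%, 70 per arm) does reproduce, at 0.814, but it concerns clinical response and does not depend on this point.

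**Step 1: inflation of one average.** Let k of the 7 assessed days be preparation or procedure days with mean loose-stool count P, and let m be the ordinary-day mean.

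Average = [(7−k)m + kP]/7 = m + k(P−m)/7.

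Neither P nor m is in the documents. Assume P = 4 to 10 and m = 1 to 3:

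- k = 1: from (4−3)/7 = 0.14 to (10−1)/7 = 1.29 stools/day
- k = 2: from 2(4−3)/7 = 0.29 to 2(10−1)/7 = 2.57 stools/day

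**Step 2: arm difference in means.** Two cases bracket the possibilities.

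- Replacement: the preparation-day count is the same whatever the arm. The difference is multiplied by (7−k)/7, which is 6/7 (14% smaller) for one day and 5/7 (29% smaller) for two.
- Additive: preparation adds the same number of stools in each arm. The addition cancels and the mean difference is unchanged.

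**Step 3: illustrative simulation**, 1,000,000 records per arm. All inputs are assumptions: baseline mean 4, SD 2; Week 12 means set at 1.5 and 2.5 stools/day before flooring at 0 (1.66 and 2.55 after); preparation-day count 8 (replacement) or about 6 extra stools (additive).

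| Case | Affected days, Week 12 / baseline | Mean difference | ≥2 reduction, two arms | Difference (points) |
|---|---|---|---|---|
| None | 0 / 0 | −0.89 | 57.7% vs 38.4% | 19.3 |
| Replacement | 1 / 0 | −0.76 | 37.8% vs 23.4% | 14.5 |
| Replacement | 2 / 0 | −0.63 | 21.4% vs 12.8% | 8.7 |
| Additive | 1 / 0 | −0.89 | 39.2% vs 22.7% | 16.5 |
| Additive | 2 / 0 | −0.89 | 23.7% vs 12.0% | 11.7 |
| Replacement | 1 / 1 | −0.77 | 50.4% vs 32.7% | 17.7 |
| Replacement | 2 / 2 | −0.64 | 41.8% vs 27.0% | 14.8 |
| Additive | 1 / 1 | −0.89 | 57.3% vs 39.0% | 18.3 |
| Additive | 2 / 2 | −0.89 | 57.0% vs 39.5% | 17.5 |

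(Differences are taken before rounding.) The replacement rows agree with Step 2: 0.89 × 6/7 = 0.76 and 0.89 × 5/7 = 0.64. In the additive case with an unaffected baseline, the standardized mean difference falls only from 0.50 to 0.485 (one day) or 0.47 (two days), through added noise.

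**Step 4: the 5-day minimum.** Excluding 2 days leaves 7 − 2 = 5, so the average can still be calculated. One preparation day, one procedure day and 48 hours after a colonoscopy (2 days) leave 7 − 4 = 3. Under the present minimum that value would be missing, so an exclusion cannot be added without also addressing the minimum.

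**The case against.** The strongest reply is that the effect is conditional. The documents do not say whether the Week 12 endoscopy comes before, on or after the visit day. Visits have a ±4-day window, and the PBMC footnote, which ties that blood draw to within about 2 days of the endoscopy, does not settle the order. An endoscopy on the visit day puts only an earlier preparation day in the window, and one after the diary week puts nothing there. This stands: a reader might infer that Week 12 counts are inflated for everyone, and the documents do not support that.

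A reader might also infer that the mean arm difference must shrink by 14% or 29%. That needs preparation-day counts to be independent of arm, which no section states; in the additive case there is no shrinkage. Nor is the fall in each arm's responder rate itself a loss of contrast. Most of it is a shift common to both arms, and only the last column of the table measures contrast.

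Baseline may be affected too. The screening endoscopy can be as close as 4 days before Week 0, and affected days there partly offset the Week 12 effect. What the baseline BSFS week contains is itself unclear, since the diary is said to start at Week 0.

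Colonoscopy is not shown to be the usual Week 12 procedure. Sigmoidoscopy is allowed, and its preparation is not described. The 48-hour exclusion therefore matters only for some participants.

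None of this supplies the missing exclusion. The Mayo rule shows that the sponsor expects such days to occur in the pre-visit week.

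**Conclusion.** The inconsistency is real and minor. SAP 5.6.1.1 averages days that SAP 5.3.1.1 and Protocol 8.1.1 discard from the same week, and no other section corrects this. When preparation falls in the window, the average can rise by k(P−m)/7: 0.14 to 1.29 stools/day for one day over the assumed ranges.

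The 2-stool reduction endpoints are the more exposed. Their arm difference narrowed in every scenario run, from 19.3 points to between 8.7 and 18.3. The mean-change endpoints lose contrast only in the replacement case. All sizes rest on assumed stool counts and assumed timing.

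The affected endpoints are exploratory with nominal p-values. A reader might extend the point to clinical response or remission at Week 12, but those use the Mayo subscores, which already carry the exclusions.

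**What to change.** In SAP 5.6.1.1, at visits with an endoscopy, remove procedure days, preparation days and the 48 hours after a colonoscopy from both numerator and denominator, matching Protocol 8.1.1 items 1b and 1d. Do the same at baseline if the screening endoscopy falls in the window.

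Identify these days from endoscopy dates and from diary or concomitant-medication records, and state what happens when no preparation date is recorded. The three days that sites tick for the Mayo subscores will not serve: an unticked day may simply be older, not ineligible.

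Keep the 5-day minimum at all other visits. Where exclusions leave fewer than 5 days at an endoscopy visit, name one fallback in advance: the 7 diary days before preparation began, or a minimum of 3 eligible days, the number the Mayo rule uses. Lowering the minimum at every visit, or also dropping antimotility and antidiarrheal days, would go beyond the problem shown here.

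The cost is a change of SAP wording and some extra programming to derive the excluded days. Some endoscopy-visit averages will rest on fewer, or slightly earlier, days.
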